### **Tier 2 Events**

Tier 2 parameters will be assessed via point estimates with 95% CIs provided for differences in the proportion of participants with events (also via the Miettinen and Nurminen method [Miettinen, O. 1985]).

Membership in Tier 2 requires that at least 4 participants in at least one treatment group exhibit the event. The threshold of at least 4 events was chosen because the 95% CI for the between-group difference in percent incidence will always include zero when treatment groups of equal size each have less than 4 events and thus would add little to the interpretation of potentially meaningful differences. Because many 95% CIs may be provided without adjustment for multiplicity, the CIs should be regarded as a helpful descriptive measure to be used in review, not a formal method for assessing the statistical significance of the between-group differences in AEs and predefined limits of change.

In addition to individual events that occur in 4 or more participants in any treatment group, the broad AE categories consisting of the proportion of participants with any AE, a drug-related AE, a serious AE, an AE which is both drug-related and serious, and discontinuation due to an AE will be considered Tier 2 endpoints.

### **Tier 3 Events**

Safety endpoints that are not Tier 1 or 2 events are considered Tier 3 events. Only point estimates by treatment group are provided for Tier 3 safety parameters.

## **Continuous Safety Measures**

For continuous measures such as changes from baseline in laboratory and vital signs parameters, summary statistics for baseline, on-treatment, and change from baseline values will be provided by treatment group in table format. In addition, summary statistics for the difference between treatment groups will also be provided.

Table 6 Analysis Strategy for Safety Parameters

Safety Tier	Safety Endpoint a	p-value	95% CI for Treatment Comparison	Descriptive Statistics		
Tier 1	ECIs	X	X	X		
Tier 2	Any AE		X	X		
	Any Serious AE		X	X		
	Any Drug-Related AE		X	X		
	Any Serious and Drug-Related AE		X	X		
	Discontinuation due to AE		X	X		
	Discontinuation due to Drug-Related AE		X	X		
	Specific AEs by SOCs and PT (incidence $\geq 4$ participants in at least one of the treatment groups)		X	X		
	PDLCs b (incidence $\geq 4$ participants in at least one of the treatment groups)		X	X		
Tier 3	Specific AEs by SOC and PT (incidence $< 4$ participants in each of the treatment groups)			X		
	PDLCs b (incidence $< 4$ participants in each of the treatment groups)			X		
	Change from Baseline Results (Labs, Vital Signs)			X		
Note: AE=adverse event; CI=confidence interval; PT=preferred term; SOC=system organ class; PDLC=pre-defined limit of change; X=results will be provided						
a Adverse Event references refer to both Clinical and Laboratory AEs. b Includes only those endpoints not pre-specified as Tier 1 or not already pre-specified as Tier-2 endpoints..						

### **9.6.3 Demographic and Baseline Characteristics**

The comparability of the treatment groups for each relevant demographic and baseline characteristic will be assessed by the use of tables and/or graphs. No statistical hypothesis tests will be performed on these characteristics. The number and percentage of participants screened and randomized and the primary reasons for screening failure and discontinuation will be displayed. Demographic variables, baseline characteristics, and prior and concomitant therapies will be summarized by treatment either by descriptive statistics or categorical tables.

## 9.7 Interim Analyses

An eDMC and Sponsor siDMC will review results of interim analyses of this study and will make recommendations for any actions to the Sponsor Executive Oversight Committee ([Table 7](#)). Recommendations by the eDMC include possible discontinuation of the study or modifications to the protocol to protect the safety of participants and actions resulting from the crossing of an efficacy or futility boundary in Phase 3. In addition to the eDMC, the Sponsor siDMC will review unblinded data from Phase 2 for purposes of approving the proposed MK-4482 dose to advance into Phase 3.

The eDMC will be supported by an unblinded statistician who will provide treatment-level results from the interim analyses. The unblinded statistician will not be involved in any discussions regarding modifications to the protocol, statistical methods, identification of protocol deviations, or data validation efforts after the interim analyses. In addition, there will be a small, cross-functional unblinded team of Sponsor personnel or delegates who will perform the exposure-response and dose-response modeling and other analyses that will be used to inform the dose selection decision process and the siDMC review. Membership on this cross-functional unblinded team will be documented in an unblinding plan and the details of the planned analyses will be outlined in the Modeling Analysis Plan document prior to initiation of the analyses. Sponsor personnel responsible for ongoing blinded data review and preparation of the final study report will not be included on the cross-functional unblinded team.

Following any decision to terminate or modify the protocol, the executive committee of the sponsor (and potentially other limited Sponsor personnel) may be unblinded to results at the treatment level in order to act on these recommendations. The extent to which individuals are unblinded with respect to results of interim analyses will be documented in a separate unblinding memo. Additional logistical details will be provided in the siDMC and eDMC Charters.

Blinding to treatment assignment will be maintained at all investigational sites. The results of interim analyses will not be shared with the investigators prior to the completion of the study. Participant-level unblinding will be restricted to an internal (or external, as appropriate) unblinded cross-functional team performing the interim analyses and dose recommendation, who will have no other responsibilities associated with the study.

There will be 3 interim analyses during the study as shown in [Table 7](#).

Table 7 Description of Interim Analyses

Interim Analysis	Timing	P001 Primary Data for Analysis	Committee Action
IA1 – Part 1 Dose Evaluation	Targeted to occur during Phase 2 after ~300 participants complete EOT combined in MK-4482-001 and MK-4482-002 a .	PK, available virologic, safety & efficacy data through EOT	eDMC recommendation for discontinuation of the study or protocol modifications Sponsor siDMC review of interim safety data and review of preliminary virology data Review by the unblinded team to inform dose selection models and analyses
IA2 - Part 1 b Dose Selection	Targeted to occur at the completion of Phase 2 after ~300 participants complete Day 29 (includes participants from IA1).	PK, safety & efficacy data through Day 29 and available virologic data	eDMC recommendation for discontinuation of the study or protocol modifications Sponsor siDMC approval of proposed MK-4482 dose for Part 2.
IA3 – Part 2 Futility/Early Efficacy	Targeted to occur during Phase 3 after ~343 of an expected 685 sustained recovery events, expected to be at approximately 50% of the full planned enrollment in the selected MK-4482 group and the placebo group in Part 2.	Safety & efficacy data through Day 29	Futility and early efficacy to be assessed by eDMC per eDMC Charter and guided by statistical criteria

eDMC=external Data Monitoring Committee; EOT=End of Treatment; IA=Interim Analysis; PK=pharmacokinetics; siDMC=standing internal Data Monitoring Committee.

a P002 is a companion MK-4482 dose-ranging study in non-hospitalized adults with COVID-19

b IA2 represents the analysis of the full Part 1 cohort of participants through Day 29.

## Interim Analyses

### **IA1 - Part 1: Dose Evaluation**

IA1 is targeted to occur during Phase 2 after data is available from ~300 participants completing EOT combined in MK-4482-001 and MK-4482-002. This IA will be used for eDMC interim data review, Sponsor siDMC review of interim safety data and review of preliminary virology data, and for unblinded team review of data to inform dose selection models and analyses.

During this interim analysis, enrollment in each study will continue in the 4 intervention groups in Phase 2 to the targeted enrollment of 300 participants.

### **IA2 - Part 1: Dose Selection**

This analysis is targeted to occur at the completion of Phase 2 after ~300 participants (~75 per group) have completed the Day 29 visit. This IA will be used to evaluate the dose/exposure-response to select the dose for Phase 3. The relationship between dose and PK (plasma NHC and PBMC NHC-triphosphate), virologic endpoints (eg, rate of virologic RNA clearance, viral RNA mutation rate), safety, and key efficacy results will be evaluated. PK and virology data from other ongoing studies of MK-4482 including MK-4482-002 will also be examined at the time of this IA to inform the Phase 3 dose selection.

Additional details regarding dose selection criteria will be described in the siDMC Charter. The dose selected for Phase 3 will be communicated directly to sites in accordance with local regulatory requirements.

Part 2 (Phase 3) enrollment will be initiated after all participants for Part 1 of this study have completed the Day 29 visit, and after the completion of the IA2 analysis.

### **IA3 – Part 2: Futility/Early Efficacy**

This study will include one planned interim analysis when ~50% of the expected sustained recovery events have occurred (~343 of an expected 685 events). The purpose of this interim analysis is to allow for early stopping in the case of futility and to allow for the initiation of marketing authorization applications in the case of a positive efficacy finding. The statistical criteria to inform this decision was developed as part of a group sequential design strategy that applies only to Part 2 (Phase 3) of the study. Given the expected rapid enrollment, there are no plans to discontinue enrollment prior to the planned final sample size in the case of a positive efficacy outcome.

The Gamma family spending function with  $\gamma = -1$  will be used to set both efficacy and futility boundaries for the primary endpoint as a guide for the eDMC. Assuming the information fraction of 50%, the non-binding futility boundary expressed on the sustained recovery rate ratio scale is 1.071 (ie, an observed point estimate for the sustained recovery rate ratio of 1.071 or lower will meet the criterion for futility). The boundary crossing probabilities for futility are 74% under  $H_0$  and 3.6% under  $H_1$  (sustained recovery rate

ratio=1.3). The p-value boundary for efficacy is 0.009, corresponding to a sustained recovery rate ratio of 1.289 (ie, an observed point estimate for the sustained recovery rate ratio of 1.289 or higher will meet the criterion for early efficacy). The boundary crossing probabilities for efficacy are 0.9% under  $H_0$  and 53% under  $H_1$  (sustained recovery rate ratio=1.3).

## 9.8 Multiplicity

Multiplicity adjustment with regard to controlling type I error for the Futility/Early Efficacy (Phase 3) Interim Analysis is described in Section 9.7.

There are two hierarchical superiority hypotheses in the Phase 3 part of this study (Section 3). A sequential testing approach will be employed to control overall type I error at 0.025, 1-sided across the primary efficacy endpoint (time-to-sustained recovery) and the key secondary efficacy endpoint (all-cause mortality). The all-cause mortality endpoint will not be tested at the interim analysis. At the end of Part 2, testing will be performed for the time-to-sustained recovery endpoint at an alpha level of 0.019. If superiority is demonstrated, the all-cause mortality endpoint will be tested at alpha level of 0.025. This strategy provides strong control of type I error at the study level. All tests are 1-sided unless otherwise noted.

## 9.9 Sample Size and Power Calculations

### 9.9.1 Sample Size and Power Calculations for Efficacy Analyses (Part 2)

The primary analysis of Phase 3 study endpoints will include ~1000 participants from Part 2 of the study (~500 for the selected MK-4482 group and ~500 for the placebo group) who meet the criteria for inclusion in the MITT population. The primary endpoint is time-to-sustained recovery. The study has overall power of 90% to demonstrate that participants treated with MK-4482 have a higher rate of sustained recovery than participants treated with placebo at an overall one-sided, 2.5% alpha-level, if the underlying constant sustained recovery rate ratio between treatment groups is 1.3.

The power and sample size are based on the following assumptions: 1) the time-to-sustained recovery follows an exponential distribution with sustained recovery rates of 0.351 and 0.270 for the MK-4482 and placebo groups, respectively, 2) a futility/efficacy interim analysis at 50% information as outlined in Section 9.7, 3) an enrollment period of 10 weeks, and 4) dropout hazard rates of 0.02 for both the MK-4482 and placebo groups, respectively. The above sustained recovery rates correspond to approximately 366 (73%) and 319 (64%) sustained recovery events for the MK-4482 and placebo groups, respectively. These are nearly identical to the recovery rates presented for remdesivir and placebo in the NEJM [Beigel, J. H., et al 2020]. The calculation was computed using both EAST and gsDesign. To meet the statistical criterion for success (one-sided p value $\leq$ 0.019 at the final analysis), the observed sustained recovery rate ratio must be approximately 1.17 or larger.

### 9.9.2 Sample Size and Power Calculations for Virology Analyses (Part 1)

The sample size for Part 1 was not determined based on a specific hypothesis for a specific endpoint. The selection of the dose to advance to Part 2 will be based on analyses of the totality of data available across the MK-4482 clinical program. Three hundred participants (75 per group) will be sufficient to provide reasonable precision to discriminate between treatment groups with regard to the virology endpoints. An important endpoint for assessing the dose-response relationship is viral RNA change from baseline in SARS-CoV-2 RNA titer, calculated as  $\log_{10}$  (post) minus  $\log_{10}$  (baseline). Approximately 80% of this cohort (60/group) is expected to have baseline viral load of at least  $10^6$  copies/mL. A 1 log-unit difference between treatment groups in the population mean is considered to be clinically relevant. [Table 8](#) provides power calculations for true log differences of 0.75 to 1.25 and for various assumptions about the true underlying standard deviation.

Table 8 Power by Detectable Difference and Standard Deviation Viral RNA Change from Baseline ( $\log_{10}$  copies/mL) N=60/group,  $\alpha=0.025$ , 1-sided

Standard Deviation	Between Group Difference ( $\log_{10}$ copies/mL)		
	-0.75	-1.00	-1.25
1.25	90%	99%	>99%
1.5	78%	95%	>99%
1.75	64%	87%	97%

### 9.9.3 Sample Size and Power Calculations for Safety Analyses (Part 2)

Part 1 (Phase 2) and Part 2 (Phase 3) of the study will be combined for the final analysis of safety endpoints. The planned sample size for safety analysis will be 575 for MK-4482 selected dose group and placebo. The probability of observing at least 1 of a particular type of AE in this study depends on the number of participants treated and the underlying percentage of participants with an AE in the study population. If the underlying incidence of an AE is 1%, there is a 99.7% chance of observing at least one AE among 575 participants in the treatment group. If no AE of that type is observed among the 575 participants in any treatment group, this study will provide 97.5% confidence that the underlying percentage of participants with the AE is < 0.64% (1 out of every 156 participants).

[Table 9](#) summarizes the percentage point differences between the 2 treatment groups that could be detected with 90% probability for a variety of hypothetical underlying incidences of an AE. These calculations assume 575 participants in each group and are based on a 2-sided 5% alpha level. The calculations are based on Farrington and Manning [Farrington, C. P. and Manning, G. 1990]. No multiplicity adjustments were made.

Table 9 Differences in Incidence of AE Rates Between the 2 Treatment Groups That Can be Detected With an ~90% Probability (Assuming 2-sided 5% Alpha Level with 575 Participants in Each Group)

Incidence of Adverse Event		Risk Difference
Placebo (%)	MK-4482 (%)	Percentage Points
1.0	4.0	3.0
5.0	10.0	5.0
10.0	16.5	6.5
20.0	28.2	8.2
30.0	39.1	9.1
40.0	49.5	9.5

Incidences presented here are hypothetical and do not represent actual adverse experiences in either group. Calculations are based on Farrington and Manning [Farrington, C. P. and Manning, G. 1990].

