#### **Part 1 (Phase 2 - Dose Ranging)**

Approximately 300 participants will be randomized in a 1:1:1:1 ratio (stratified per Section 6.3.2) into 1 of the following 4 blinded treatment groups ([Figure 1](#)):

- MK-4482 200 mg (n~75)
- MK-4482 400 mg (n~75)
- MK-4482 800 mg (n~75)
- Placebo (n~75)

The final dose selection will be based on analysis(es) of data from this study in combination with the totality of data available across the MK-4482 clinical program prior to initiating Part 2 (Sections 4.3.3 and 9.7).

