### **9.5 Analysis Populations**

#### **9.5.1 Efficacy Analysis Populations**

The MITT population will serve as the primary population for the analysis of efficacy data for both parts of this study. The MITT population consists of all randomized participants who received at least 1 dose of study intervention. Part 1 (Phase 2) and Part 2 (Phase 3) of the study will be analyzed separately for efficacy endpoints. Therefore, the MITT population for Part 2 will not include Part 1 participants, and vice versa.

A supportive analysis using the Per-Protocol population will be performed for primary and secondary efficacy endpoint(s) for Part 2. The Per-Protocol population excludes participants due to deviations from the protocol that may substantially affect the results of the primary efficacy endpoint.

The final determination on protocol deviations, and thereby the composition of the Per-Protocol population, will be made prior to the final unblinding of the database and will be documented in a separate memo.

Participants will be included in the treatment group to which they are randomized for the analysis of efficacy data using both the MITT and Per-Protocol populations.

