### **9.5.2 Safety Analysis Populations**

Safety Analyses will be conducted in the APaT population, which consists of all randomized participants who received at least one dose of study treatment. Participants will be included in the treatment group corresponding to the study treatment they actually received for the analysis of safety data using the APaT population. This will be the treatment group to which they are randomized except for participants who take incorrect study treatment for the entire treatment period; such participants will be included in the treatment group corresponding to the study treatment actually received. Part 1 (Phase 2) and Part 2 (Phase 3) of the study will be combined for the final analysis of safety endpoints. The data presentations will focus on the selected dose group for MK-4482 and placebo.

At least one laboratory value or vital sign obtained subsequent to at least one dose of study treatment is required for inclusion in the analysis of the respective safety parameter. To assess change from baseline, a baseline measurement is also required.

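### The final safety comparison reuses the Part 1 selected-dose participants whose safety data helped choose the dose, and no final Part 2-only comparison is prespecified (minor)

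*Combined protocol and SAP*

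**What the plan says.** Section 9.9.3 pools the two parts for safety: "Part 1 (Phase 2) and Part 2 (Phase 3) of the study will be combined for the final analysis of safety endpoints". The resulting size is given as "The planned sample size for safety analysis will be 575 for MK-4482 selected dose group and placebo". Section 9.5.2 repeats the pooling and adds: "The data presentations will focus on the selected dose group for MK-4482 and placebo".

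Section 9.5.1 does the opposite for efficacy: "Part 1 (Phase 2) and Part 2 (Phase 3) of the study will be analyzed separately for efficacy endpoints".

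The Part 2 dose is chosen at IA2 from the full Part 1 cohort through Day 29 (Section 9.7 and Table 7). The list of results to be related to dose covers PK and virology and ends with "viral RNA mutation rate), safety, and key efficacy results will be evaluated". The criteria themselves are left to the siDMC Charter.

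The Tier 1 tests in Section 9.6.2 use the Miettinen and Nurminen method without stratification. Sections 9.5.2, 9.6.2 and 9.9.3 contain no final safety comparison restricted to Part 2, none by part, and no sensitivity analysis for the pooling. Part 2 safety data are seen separately at IA3, by the eDMC, at about half of the expected recovery events.

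**The concern.** An arm whose Part 1 participants happened to have more adverse events is less likely to be taken forward if safety counts in the choice. The arm that is taken forward then carries a favourable chance deviation into the final pool. The Part 1 placebo arm carries none, because it is retained whatever the choice. The pooled active-minus-placebo difference can therefore be shifted towards less harm.

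Safety is a primary objective of the trial. The pooled contrast is the only final safety comparison that the plan specifies, so a reader of the final report would have no prespecified contrast that is independent of the dose choice. For efficacy, the separation of the parts already provides one.

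**Working it through.** **Inputs.** Part 1 has three active arms and placebo, each of about 75 (Section 4.1, for example "MK-4482 800 mg (n~75"). Part 2 has about "500 for the selected MK-4482 group and ~500 for the placebo group" (Section 9.9.1). The Table 9 calculations "are based on a 2-sided 5% alpha level".

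**1. The plan's own figures.**
- Size: 75 + 500 = 575 per group.
- Chance of at least one event at 1% incidence: 1 − 0.99^575 = 99.7%, as stated.
- Zero-event upper bound: 1 − 0.025^(1/575) = 0.64%, or 1 in 156, as stated.
- Table 9, 20% v 28.2%: the mean rate is 0.241. The null standard error is √(2 × 0.241 × 0.759/575) = 0.02522. The alternative standard error is √((0.20 × 0.80 + 0.282 × 0.718)/575) = 0.02511. Power = Φ[(0.082 − 1.96 × 0.02522)/0.02511] = Φ(1.30) = 90%.
- The six Table 9 rows give 89.7% to 90.4%.

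All stated figures reproduce.

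**2. Share open to selection.** 75/575 = 13% of the selected-dose arm.

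**3. Worst-case shift with no true difference.** This rests on an assumption that is not in the documents: all three doses have the same true rate p, and the arm with the lowest count of the endpoint is always chosen. The expected lowest count of three is Σ P(X > k)³ over k = 0 to 74, with X binomial(75, p). The shift in the chosen arm is that sum divided by 75, minus p. Multiplying by 75/575 gives the pooled shift. The standard error of the pooled difference is √(2p(1 − p)/575).

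| AE rate | Shift, chosen Part 1 arm (points) | Shift, pooled difference (points) | SE (points) | Shift/SE |
|---|---|---|---|---|
| 1% | −0.80 | −0.10 | 0.59 | 0.18 |
| 5% | −2.04 | −0.27 | 1.29 | 0.21 |
| 10% | −2.86 | −0.37 | 1.77 | 0.21 |
| 20% | −3.86 | −0.50 | 2.36 | 0.21 |
| 30% | −4.44 | −0.58 | 2.70 | 0.21 |
| 40% | −4.77 | −0.62 | 2.89 | 0.22 |

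If harm is real and equals the Table 9 differences (active rates 4% to 49.5%), the same formula gives 0.24 to 0.64 points of understatement.

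**4. Effect on inference** (simulation, 400,000 trials per row, same worst case).
- No true difference, AE rates of 5% or more: the 95% interval lies wholly below zero in about 3.9% of trials and wholly above zero in about 1.4%, against a nominal 2.5% on each side.
- At the Table 9 differences, detection is 90–93% for an unselected pool of 575, 86–90% for the pool with worst-case selection, and 86–89% for Part 2 alone.

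**5. Less extreme selection.** On a normal approximation, the shift scales with the correlation between the endpoint's arm-level rate and whatever decided the dose. At 20% incidence an assumed correlation of 0.3 gives 0.3 × 0.50 = 0.15 points. A correlation of zero gives none.

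**6. Part 2 alone (500 per group).**
- Zero-event bound: 1 − 0.025^(1/500) = 0.74%, or 1 in 136.
- Differences detectable with 90% power: 3.3, 5.5, 7.0, 8.8, 9.8 and 10.2 points, against 3.0, 5.0, 6.5, 8.2, 9.1 and 9.5 in Table 9.
- Interval width relative to the pool: √(575/500) = 1.07.

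**The case against.** The strongest reply is that the worst case is not the plan's rule. Section 9.6.1 calls early viral RNA results important for the dose decision. Section 9.6 plans MCP-MOD and exposure-response modelling. Section 9.7 brings in PK and virology from other studies, and Section 4.1 refers to the whole clinical programme. One dose is chosen once, so its arm cannot be expected to have the lowest observed rate for every adverse event. The worst case fits only an endpoint that decided the dose by itself. Tier 1 consists of three laboratory-defined events for which the documents give no rates. If these are uncommon, the 1% row is the relevant one. All of this stands, and it limits the size of the point but does not remove it.

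A reader might infer more than the documents support, in four ways:
- **That Part 2 safety is never looked at separately.** The eDMC receives it at IA3 and reviews accumulating safety data periodically (Section 4.1). What is missing is a final, reported contrast.
- **That the Tier 1 p-values lean towards no harm as a matter of course.** They do so only to the extent that observed safety drove the choice, and the rule is in a charter outside these documents.
- **That pooling weakens detection of harm, or that 9.9.3 is wrong.** Even under worst-case selection the pool performs about as well as Part 2 alone, and without selection it does better. Every stated figure reproduces.
- **That benefit and risk are read in different people.** About 87% of the pooled safety arm (500/575) are Part 2 participants.

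Pooling does not itself confound by part either, because selected dose to placebo is 1:1 in both parts. The Tier 2 intervals are described in Section 9.6.2 as descriptive.

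**Conclusion.** The point holds as a minor one. The same selected-dose Part 1 participants inform the dose choice and then enter the final safety comparison, against a placebo arm that was not selected, with no final Part 2-only comparison prespecified. Any resulting bias runs towards understating harm.

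Its size lies between about zero and the step 3 ceiling, which is about 0.2 standard errors. The ceiling assumes equal true rates across doses and a choice made solely on the endpoint in question. Where in that range the trial falls cannot be settled from the documents. The gain from acting is a contrast free of dose selection, in the participants who supply the efficacy result. It is not a gain in power.

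**What to change.** Keep the pooled safety analysis as planned. In Sections 9.5.2 and 9.6.2, prespecify a supportive Part 2-only APaT summary (about 500 v 500) of the Tier 1 events of clinical interest and the Tier 2 broad AE categories, displayed beside the pooled result. Settling this before Part 1 is unblinded avoids any appearance that the presentation was chosen after the data were seen.

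The cost is a short addition to the SAP and one extra set of tables, with intervals about 7% wider than the pooled ones. Adding the n = 500 figures from step 6 to Section 9.9.3 is optional, since nothing stated there is wrong.
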